4.4.4. Exposure

The exposure of interest in this study is first ever tofacitinib use after any prior RTX use. All patients in the study will be classified as exposed.

4.4.5. Study Outcomes

4.4.5.1. Aim 1: Characterize Patients at tofacitinib initiation

4.4.5.1.1. Primary Outcome:

- Aim 1 is to characterize patients at tofacitinib initiation. All variables listed in [Section 4.4.6](#) below will be summarized for this aim.

4.4.5.2. Aim 2: Describe change in 6-month outcomes

4.4.5.2.1. Primary Outcome:

- Change in Clinical Disease Activity Index (CDAI)

4.4.5.2.2. Secondary Outcomes:

- Achievement of Minimum Clinically Important Difference (MCID) (Curtis et al., 2015)⁵: (change in CDAI from baseline to follow-up = Δ CDAI)

| CDAI at Index | MCID to Define Improvement in Disease Activity at FU Visit If Δ CDAI>MCID |
|----------------------|---|
| | |
| Low: CDAI≤10 | 1 |
| Moderate: 10>CDAI≤22 | 6 |
| High>22 | 12 |

- Change in HAQ
- Change in patient pain
- Change in patient fatigue
- Number (%) of tofacitinib discontinuations prior to or at 6-month visit

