9.4.2. Study Outcomes

Objective 1: Characterize Patients at tofacitinib initiation

Primary Outcome:

- Objective 1 is to characterize patients at tofacitinib initiation. All variables as outlined in the SAP will be summarized for this aim.

Objective: Describe change in 6-month outcomes.

Primary Outcome:

- Change in CDAI.

Secondary Outcomes:

- Achievement of Minimum Clinically Important Difference (MCID):² (change in CDAI from baseline to follow-up = Δ CDAI).

CDAI at Index	MCID to Define Improvement in Disease Activity at FU Visit If ΔCDAI>MCID
Low: CDAI \leq 10	1
Moderate: 10 $>$ CDAI \leq 22	6
High $>$ 22	12

- Change in HAQ.
- Change in patient pain.
- Change in patient fatigue.
- Number (%) of tofacitinib discontinuations prior to or at 6-month visit.

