4.4.6.4. RA Disease Activity Measures (physician-derived elements)

- Clinical Disease Activity Index (CDAI): continuous range 0-76
- CDAI category: remission [0-2.8], low (2.8-10], moderate (10-22], high (22-76]
- MD global assessment VAS (0-100)
- Tender joint count (0-28)
- Swollen Joint count (0-28)

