4.4.7. Analysis Plan

4.4.7.1. Aim 1: *Describe the characteristics of tofacitinib initiators with a history of rituximab exposure, at time of tofacitinib initiation*

Descriptive statistics for the variables listed in [Section 4.4.6](#) will be provided for all tofacitinib initiators with history of rituximab use. All variables will be measured at the index visit, as defined above. Categorical covariates will be described by frequency distribution while continuous covariates will be expressed in terms of their mean and standard deviation or median and interquartile range (IQR) as appropriate.

4.4.7.2. Aim 2: *Describe 6-month outcomes for tofacitinib initiators with a history of rituximab exposure*

Descriptive statistics for index visit characteristics will be provided for the subsets of patients included in this Aim (tfacitinib initiators who have a 6-month follow-up visit), as described in Aim 1.

Analyses of outcomes at the 6-month follow-up after tofacitinib initiation will be descriptive. Primary and secondary outcomes will be described as mean absolute differences for continuous measures and as frequencies and proportions for dichotomous measures, with corresponding 95% confidence intervals (95% CI). Mean absolute difference will be defined as the value at the 6-month follow-up visit minus the value at baseline. The number of patients that discontinue tofacitinib will also be summarized. A subgroup analysis related to the outcomes for Aim 2 will be carried out focused on patients who used rituximab immediately prior to tofacitinib.

All analyses will be conducted using Stata Release 16 (StataCorp LLC, College Station TX) and/or R Version 4.0.3 (The R Foundation for Statistical Computing, Vienna Austria).

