7. Efficacy reasons: IR-inadequate initial response, FR-failure to maintain initial response; Safety reasons: SE-serious side effect, ME-minor side effect; Other reasons: FE-fear of future side effect, TI-temporary interruption, PP-patient preference, IC-to improve compliance, IT-to improve tolerability, FA-frequency of administration, RA-route of administration, AM-alternate mechanism of action, OT-other; Insurance reasons: CP-co-pay/patient cost, DI-denied by the insurance; AD-Active disease (for starts or increasing dose); DW-Patient doing well.

*See [Appendix A](#) for comprehensive list of definitions

Table 2: Reasons for Discontinuation of Rituximab among Patients who Discontinued at or after Enrollment in the Registry

| | N = |
|---|------------|
| Reasons for discontinuing rituximab, categorical, n (%)¹ Efficacy, n/ N1 (%) Safety, n/ N1 (%) Insurance, n/ N1 (%) Active disease, n/ N1 (%) Other reasons, n/ N1 (%) | |

¹ Efficacy reasons: IR-inadequate initial response, FR-failure to maintain initial response; Safety reasons: SE-serious side effect, ME-minor side effect; Other reasons: FE-fear of future side effect, TI-temporary interruption, PP-patient preference, IC-to improve compliance, IT-to improve tolerability, FA-frequency of administration, RA-route of administration, AM-alternate mechanism of action, OT-other; Insurance reasons: CP-co-pay/patient cost, DI-denied by the insurance; AD-Active disease (for starts or increasing dose); DW-Patient doing well.

Table 3: Change in Outcomes from Baseline to 6months Follow-up

| Outcomes: | N= | |
|------------------------------------|-----------|--------|
| | Mean (SD) | 95% CI |
| Δ CDAI | | |
| Achievement of MCID (n, %, 95% CI) | | |
| Δ HAQ | | |
| Δ Patient pain | | |
| Δ Patient fatigue | | |

Table 4: Change in outcomes from baseline to 6-months follow-up restricted to patients with RTX as immediate prior treatment

| Outcomes: | N= | | | | |
|--|----|--------------------|-------------------|----------------------|--------|
| | N | Baseline Mean (SD) | 6-month Mean (SD) | Difference Mean (SD) | 95% CI |
| CDAI | | | | | |
| Achievement of MCID (n,%) ¹ | | | | | |
| HAQ | | | | | |
| Patient pain VAS (0-100) | | | | | |
| Patient fatigue VAS (0-100) | | | | | |

¹ restricted to patients who had greater than remission (e.g., CDAI \geq 2.8) at baseline

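### The MCID responder rule is misprinted: the SAP's sign counts a rise in CDAI as improvement, and the moderate row in both documents leaves baselines above 10 up to 22 without a threshold

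*SAP*

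**What the plan says.** SAP 4.4.5.2.2 lists MCID achievement as a secondary outcome of Aim 2. It defines ΔCDAI as the "change in CDAI from baseline to follow-up" and gives a table headed "MCID to Define Improvement in Disease Activity at FU Visit If" ΔCDAI is greater than the MCID. The thresholds are 1 (low, CDAI ≤ 10), 6 (moderate) and 12 (high, above 22). The moderate row is printed "Moderate: 10>CDAI≤22".

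Protocol 9.4.2 prints the same definition, thresholds and moderate inequality.

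Three other places in the SAP bear on how the rule is read:

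- 4.4.7.2 fixes the order of subtraction for continuous outcomes: "Mean absolute difference will be defined as the value at the 6-month follow-up visit minus the value at baseline". The Protocol has no such sentence.
- 4.4.6.4 gives the scale, "Clinical Disease Activity Index (CDAI): continuous range 0-76", and the categories, "remission [0-2.8], low (2.8-10], moderate (10-22], high (22-76" with 76 included. Lower is better, and moderate means above 10 up to and including 22.
- Table 3 lists ΔCDAI directly above MCID achievement. Table 4 repeats MCID achievement for patients whose immediate prior treatment was rituximab, and its footnote limits that row to patients above remission at baseline.

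**The concern.** There are two separate faults.

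**Sign.** If ΔCDAI is follow-up minus baseline, a fall is negative. All three thresholds are positive, so the printed condition can be met only by a patient whose CDAI rose, which is the opposite of the improvement named in the column heading.

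**Band.** The moderate row asks for a CDAI that is both below 10 and at most 22. That is simply a CDAI below 10. The range the row is meant to cover receives no threshold, and the low range receives two.

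MCID achievement is the only response outcome listed for Aim 2, and SAP 4.3 says the study will provide evidence on effectiveness. A programmer or checker who works from the printed rule cannot apply it to moderate disease, and would label worsening as improvement elsewhere.

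**Working it through.** **Inputs.** ΔCDAI, thresholds and rows from SAP 4.4.5.2.2; order of subtraction from SAP 4.4.7.2; range and categories from SAP 4.4.6.4. The plan states no expected MCID rate, so there is no figure to reproduce.

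**Step 1: direction.** Put Δ = follow-up − baseline and apply Δ > MCID.

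| Baseline → 6 months | Δ | Printed rule | Baseline − 6 months > MCID, moderate = (10, 22] |
|---|---|---|---|
| 30 → 10 | −20 | not above 12: fails | 20 > 12: achieved |
| 30 → 43 | +13 | above 12: improvement | −13: fails |
| 16 → 8 | −8 | no row applies | 8 > 6: achieved |
| 8 → 5 | −3 | fails on 1 and on 6 | 3 > 1: achieved |
| 8 → 11 | +3 | improvement on 1, fails on 6 | −3: fails |

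Count all whole-number pairs from 0 to 76 that meet the printed rule on any matching row:

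- Baselines 0–10 (lowest threshold 1): 75 − b qualifying follow-up values each, so 11 × 75 − 55 = 770.
- Baselines 11–22: no row, so 0.
- Baselines 23–63 (threshold 12): 64 − b values each, so 41 + 40 + … + 1 = 861. Above 63 none is possible.

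The total is 770 + 861 = 1,631 pairs. In none of them did CDAI fall or stay the same. With positive thresholds, Δ > MCID and −Δ > MCID cannot both hold, so the printed sign and the intended rule never select the same patient.

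**Step 2: coverage.** On a grid of 0.0 to 76.0 in steps of 0.1 (761 values), baselines 10.1 to 22.0 (120 values) match no row. Baselines 0.0 to 9.9 (100 values) match both low (1) and moderate (6). With the moderate row as 10 < CDAI ≤ 22, every value has exactly one threshold.

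**Step 3: scale (illustrative only).** The documents give no CDAI mean or SD, so these inputs are assumptions. Baseline is normal, truncated to 0–76, and change is normal. Each scenario has 2 million draws. Follow-up outside 0–76 is either clipped or redrawn. Both columns use corrected bands, so the gap isolates the sign; gaps come from unrounded rates.

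| Baseline mean, SD; change mean, SD | Clipped: corrected / reversed / gap | Redrawn: corrected / reversed / gap |
|---|---|---|
| 24, 13; −6, 12 | 40.3 / 11.9 / 28.4 | 31.5 / 16.7 / 14.9 |
| 24, 13; −3, 12 | 31.5 / 17.2 / 14.3 | 24.6 / 21.4 / 3.2 |
| 20, 12; −5, 10 | 38.6 / 11.7 / 27.0 | 29.8 / 16.9 / 12.9 |
| 26, 14; −8, 13 | 45.6 / 10.1 / 35.6 | 35.9 / 14.9 / 21.1 |

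(Rates in %, gaps in percentage points.) The bounds weaken the assumed change: realised means are −2.3 to −6.7 with clipping and −1.0 to −4.7 with redrawing.

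Between 27% and 38% of patients start in the band with no threshold. They supply 30–47% of the achievers under the corrected rule.

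A second set of assumptions (baseline mean 18–26, SD 12; change mean −3 to −9, SD 11; baseline and follow-up both clipped) gives 28–51% corrected against 6–20% with the sign reversed.

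**Step 4: related inconsistencies.** Table 1 puts scores of exactly 10 and 22 in the higher category, and Table 1 and the Table 4 footnote put exactly 2.8 outside remission; 4.4.6.4 does the opposite in each case. Table 4 excludes baseline remission from MCID, and Table 3 states no exclusion. In the four scenarios, that exclusion moves the corrected rate by only −0.2 to +0.7 points.

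**The case against.** The strongest reply is that no competent analyst would be misled. The subtraction in SAP 4.4.7.2 is given for continuous measures, while MCID achievement is dichotomous. The responder table does not refer to that section, and its heading names improvement, so the threshold is naturally read as the size of an improvement. For the band, the row is labelled moderate, its neighbours leave only (10, 22], and 4.4.6.4 prints that range. The outcome is secondary and descriptive, with no hypothesis test. A reversed result would probably be noticed beside mean ΔCDAI in Table 3.

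Much of this stands. The sign conflict is an inference from the words defining ΔCDAI and from the shared symbol. It is weaker in the Protocol, which prints no subtraction. The intent can be recovered in both cases, and nothing shows that the analysis will be wrong. The simulated rates depend heavily on the assumptions: the gap runs from 3 to 36 points.

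It does not make the rule correct as written. Nothing in the responder definition reverses the sign. Reading the term mean absolute difference as a magnitude does not help either, because rises above the threshold would still count as improvement. The SAP also prints three versions of the moderate band (the MCID table, 4.4.6.4 and Table 1), so the correction should be stated and not left to the programmer.

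**Conclusion.** The concern holds. As printed in the SAP, the responder rule selects only patients whose CDAI rose. In both documents the moderate row gives no threshold to baselines above 10 up to 22 and gives two to baselines below 10. These conclusions follow from the text alone; the sign conclusion also needs ΔCDAI to be read as follow-up minus baseline, which only the SAP states.

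This is a specification error that should be fixed. It is confined to MCID achievement in Tables 3 and 4, and the Aim 2 primary outcome, mean change in CDAI, is unaffected. The size of any error in a reported rate cannot be fixed from the documents. The simulated rates (25–46% corrected, 10–21% with the sign reversed) only show that the difference could be material.

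**What to change.** In SAP 4.4.5.2.2 and Protocol 9.4.2:

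1. Define achievement as (baseline CDAI − 6-month CDAI) > MCID.
2. Print the moderate row as 10 < CDAI ≤ 22. This agrees with the low and high rows already in the table and with SAP 4.4.6.4.

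As minor edits at the same time, align the cut-points in Table 1 and the Table 4 footnote with 4.4.6.4, and state one MCID denominator for Tables 3 and 4. The documents do not settle whether patients in remission at baseline belong in it, so the sponsor has to choose and say so.

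The cost is two wording edits in each document and small table-shell edits in the SAP, with no new data or added analysis. Protocol 9.7 lets the SAP modify the protocol and calls for an amendment only for major changes to primary endpoints. The SAP correction could therefore go first, with the Protocol text corrected and logged so that the two agree.

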4.4.2. Study Population of Interest

The primary analysis (Aim 1) will include patients that initiated tofacitinib at or post enrollment into the Registry and after tofacitinib approval, and who have any prior use of RTX. The secondary analysis (Aim 2) will include the subset of patients from the primary analysis who also have a 6-month follow-up visit (as defined below) after tofacitinib initiation with clinical and patient reported outcomes.

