For patients who discontinue tofacitinib prior to 6 months window, the clinical or patient-reported outcome (listed in Section 4.4.5.2) will be imputed via last observation carried forward (LOCF), using only registry visits that occur before the discontinuation. Specifically, outcomes observed at a registry visit in the 6-month window will use data collected at that visit with the following exception. Patients that discontinue tofacitinib at a registry visit prior to the six month window will have the outcomes collected at that registry visit carried forward as the outcomes in the 6-month window. A patient that discontinues tofacitinib between registry visits will have the outcomes collected at the registry visit prior to the discontinuation carried forward as the 6-month outcome.

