4.4.8. Missing Data

Missing data could be expected for demographic characteristics (e.g., age, etc.); however, the number of patients with missing data is expected to be very small, and is not expected to vary systematically. For every variable, the number of patients with nonmissing information will be reported. Effective sample size may differ across outcome measures due to missingness; because missingness is expected to be very minimal, no imputation of missing values will be applied.

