4.5.2. Limitations

The CorEvitas RA Registry used in this research includes a sample of adults with RA that are not necessarily representative of all adults with RA in the US, or of those in emerging markets outside the US. In particular, these are patients with RA with clinical visits with rheumatologists.

Most importantly for this study, in the US rituximab is typically prescribed as a later line therapy, after failure of one or more TNFi. It is also given as a first-line bDMARD to patients with contraindications to TNF inhibitors (e.g., interstitial lung disease) [1]. This may differ from prescribing patterns in countries other than the US, which could influence the generalizability of the results to RA patients outside of the United States.

In addition, history of medication use prior to enrollment is derived from what is reported by patients and their current rheumatologist within the registry. Since the registry is not based on an inception cohort, patients may not be able to recall their entire medication history, leading to possible mischaracterization regarding prior use of RTX. The registry captures physician-reported prescribing, but there are no measures of patient adherence. Confounding by indication can occur when factors that determine

physicians' selection of a particular treatment (e.g. disease severity, comorbidities) also affect the outcome being studied. There are certain conditions (TB, lymphoma) that would prompt the prescribing of rituximab. This population could have different outcomes than a population without these comorbidity histories.

Patients who maintain treatment at 6 months may have different outcomes compared to the outcomes those who discontinue or switch would have had, had they not discontinued/switched. This study takes steps to mitigate this potential bias by including values at follow-up for those who discontinue treatment and values at switch for those who switch, as described above.

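### The Aim 2 tofacitinib discontinuation percentage has no settled denominator: the SAP and protocol define conflicting sets, and under some of them entry depends on having stopped

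*SAP*

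**What the plan says.** **The outcome.** SAP 4.4.5.2 lists "Number (%) of tofacitinib discontinuations prior to or at 6-month visit" among the Aim 2 secondary outcomes. SAP 4.4.7.2 promises counts and proportions with 95% confidence intervals for all dichotomous Aim 2 outcomes, then adds: "The number of patients that discontinue tofacitinib will also be summarized". Neither place names a denominator. The shells of Tables 3 and 4 have rows for CDAI, MCID, HAQ, pain and fatigue, but none for discontinuation.

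**The population in the SAP.** SAP 4.4.2 limits Aim 2 to Aim 1 patients "who also have a 6-month follow-up visit (as defined below) after tofacitinib initiation with clinical and patient reported outcomes". SAP 4.4.7.2 repeats the condition: "initiators who have a 6-month follow-up visit".

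**The population in the protocol.** Under Objective 2, protocol 9.2.1 gives four ways in:
- (a) still on tofacitinib, with a 6-month visit;
- (b) stopped before the 6-month visit, attended that visit, and took no new biologic in between;
- (c) stopped at a visit that falls in the 6-month window or before it;
- (d) any stop before the window, for a sensitivity analysis only.

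The current SAP contains no such sensitivity analysis.

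**Handling of stoppers.** Under SAP 4.4.3.3, outcomes of patients who stop before the window "will be imputed via last observation carried forward (LOCF), using only registry visits that occur before the discontinuation". It continues: "Patients that discontinue tofacitinib at a registry visit prior to the six month window will have the outcomes collected at that registry visit carried forward". A stop between visits takes the value from the visit before the stop. Neither rule asks for a later visit.

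**Two related statements.** SAP 4.5.2 still describes the study as "including values at follow-up for those who discontinue treatment and values at switch for those who switch". SAP 4.4.8 says that "because missingness is expected to be very minimal, no imputation of missing values will be applied".

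**The concern.** A descriptive percentage is only as clear as its denominator. Here a patient who stays on tofacitinib must attend in the window to be counted. A patient who stops early may be counted on an earlier visit, depending on which section the analyst follows. Where that happens, having the event is itself a way into the denominator.

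Two analysts working from the same data and documents could therefore report different discontinuation percentages, each with a confidence interval that reflects sampling error only. A reader could not tell which set was used, or whether the figure is too high or too low for rituximab-experienced initiators. The study is meant to inform healthcare providers, and this is its only planned summary of how often patients come off the drug.

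**Working it through.** **Step 1: put the rules side by side.** Assume CDAI was measured at baseline and at the visits named.

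| Patient | SAP 4.4.2 / 4.4.7.2 | Protocol 9.2.1 | SAP 4.4.3.3 |
|---|---|---|---|
| Stays on drug, visit in window | in | in, by (a) | observed value |
| Stays on drug, no visit in window | out | out | no value |
| Stops at a month-2 visit, no later visit | out | in, by (c) | month-2 value carried forward |
| Stops between visits before the window, no later visit | out | sensitivity analysis only, by (d) | value from the visit before the stop |
| Stops between visits before the window, starts a new biologic, attends in window | in | not by (b) or (c); sensitivity analysis only, by (d) | value from the visit before the stop |

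Rows 2 and 3 show the asymmetry. Neither patient has a window visit, and only the stopper has a way in.

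**Step 2: direction between readings.** Let *N* be the patients with a 6-month visit, *d* the stoppers among them, and *m* the early stoppers without a window visit who are added by item (c) or by the 4.4.3.3 reading.

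- With a visit required of everyone: *d / N*.
- With early stoppers added: *(d + m) / (N + m)*.

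Since *d ≤ N*, the second is never below the first, because each added patient counts in both numerator and denominator. This concerns the addition of those patients only. Item (b) works the other way by removing some switchers (row 5), so the full protocol set (a) to (c) has no fixed direction against SAP 4.4.2.

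**Step 3: inputs from the documents.** There is no sample-size calculation or expected discontinuation rate to reproduce. SAP 4.4.9 gives a feasibility count at 31 March 2021: 390 initiators, about 376 with baseline CDAI, and about 107 with CDAI at baseline and 6 months.

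- 107 / 376 = 28.5%.
- 376 − 107 = 269, and 269 / 376 = 71.5% without both values.

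This count was made without the LOCF rule. Some of the 269 may not yet have reached 6 months, and a later data cut is planned.

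**Step 4: illustration.** Take *N* = 107 as a stand-in for the SAP 4.4.2 set. The values of *d* and *m* are assumed, since the documents give none.

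| *d* | *m* = 0 | *m* = 10 | *m* = 20 | *m* = 40 |
|---|---|---|---|---|
| 21 | 21/107 = 19.6% | 31/117 = 26.5% | 41/127 = 32.3% | 61/147 = 41.5% |
| 32 | 32/107 = 29.9% | 42/117 = 35.9% | 52/127 = 40.9% | 72/147 = 49.0% |

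The table shows how sensitive the figure is to the choice of set. It does not estimate actual bias.

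**Step 5: the imputation wording.** SAP 4.4.3.3 imputes outcomes by LOCF. SAP 4.4.8 rules out imputation in a sentence that covers outcome measures, and it makes no exception. The two conflict as worded. This is separate from the denominator and lends it no support.

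**The case against.** The strongest reply is that the denominator has a clear default. The outcome sits under Aim 2, and the SAP defines the Aim 2 population twice in the same terms. On this view SAP 4.4.3.3 assigns values and is not an eligibility rule. It also has work to do inside the SAP 4.4.2 set: a patient who stops at a month-2 visit and attends again at month 6 receives the month-2 value. SAP 4.4.8 promises the non-missing count for every variable, and Figure 1 will show selection, so the denominator should be visible. Tables 3 and 4 are titled as change tables, so a missing row there is weak evidence. Protocol 9.7 allows the SAP to modify the protocol's plans.

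Much of this stands. A reader might infer that the SAP itself states that stoppers enter without a 6-month visit. It does not: 4.4.3.3 only implies it, and the explicit wording is protocol 9.2.1(c). A reader might also take the added sentence in SAP 4.4.7.2 to promise a bare count. The same section already promises a proportion with an interval. Nor is Table 1 limited to baseline items, since its shell asks for duration of tofacitinib use, although that gives no count of stops.

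The default still does not settle the matter. The protocol's inclusion criteria remain in force with a different set, and no SAP text says that 4.4.2 replaces them. SAP 4.4.3.3 assigns 6-month outcomes to patients whom 4.4.2 would exclude, without restricting itself to those with a later visit. A visible count shows how many were used, but not which rule selected them.

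It is also fair to say that a time-to-stop risk in all initiators is a new quantity for a descriptive study. It is recommended because it removes the dependence of entry on the outcome. Stating one denominator is the minimum.

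**Conclusion.** The point holds as an unresolved conflict over the denominator of one descriptive secondary outcome. It should be corrected, but it affects no sample size or error rate. Two things are firm: the sections describe different sets, and adding early stoppers who lack a window visit can only leave the percentage unchanged or raise it.

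The size cannot be obtained from the documents. In the illustration the gap runs from 6.0 points (29.9% to 35.9%) to 21.9 points (19.6% to 41.5%), and it rests wholly on assumed counts. The 28.5% with CDAI at both times shows that selection into Aim 2 could be substantial, with the limits given for that count.

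Two stronger conclusions are tempting and not supported:
- **That the percentage overstates the true discontinuation risk.** Requiring a visit could select for or against stoppers, and the documents give no rates by which to judge.
- **That 107 of 376 disproves the expectation of very little missing data in SAP 4.4.8.** That expectation can be read as item missingness among included patients, and a 6-month visit is partly an entry condition.

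The SAP 4.4.8 conflict with the LOCF rule and the outdated SAP 4.5.2 text are real, but they are wording corrections.

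**What to change.** 1. **Report discontinuation in all Aim 1 initiators** as a 6-month risk from tofacitinib start, censored at last registry contact, with a 95% confidence interval and the number whose status at 6 months is unknown. If the Aim 2 percentage is kept, show it beside this figure with its denominator, in an added table row.
2. **Describe one Aim 2 population** in SAP 4.4.2, 4.4.3.3 and 4.4.7.2 and in protocol 9.2.1, including what becomes of item (d) now that its sensitivity analysis is absent. Update SAP 4.5.2 to match 4.4.3.3.
3. **Correct SAP 4.4.8** so that its no-imputation statement excepts the LOCF rule in 4.4.3.3.

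The cost is SAP wording, one table row and a small analysis that should need no new data collection, since the Table 1 shell already asks for duration of tofacitinib use. Aligning protocol 9.2.1 may need a protocol amendment. The downside is that the 6-month risk relies on non-informative censoring, which may fail if leaving the registry is related to stopping the drug. The assumption should be stated, and the unknown-status count lets a reader judge how much rests on it.

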4.4. Research Design

This will be a retrospective analysis of a prospective observational cohort using The CorEvitas RA Registry. This study will describe demographic and clinical characteristics of adult patients with RA initiating tofacitinib with a history of RTX use. This study will also describe changes in clinical and patient reported outcomes over time. The index date will be defined as the date of tofacitinib initiation at or after enrollment in the registry; initiation is defined as first ever use of tofacitinib.

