4.4.3. Time Period Definitions

The CorEvitas RA Registry is an observational registry and therefore collects patient and physician data at patient clinical visits with the rheumatologist. Unlike clinical studies, visits are not timed at exact uniform time periods. Thus, time period definitions for the current study need to accommodate this unique feature of observational registries.

“Index visit” is defined as the visit when tofacitinib was initiated, i.e. first ever use of tofacitinib. Only initiations at or after enrollment into the Registry are included.

A “6-month” follow-up is defined as a clinical visit to the rheumatologist 3 to 9 months from the enrollment visit in accordance with the Registry protocol.

4.4.3.1. *Initiations between visits*

If tofacitinib is initiated between visits, then baseline variables from the visit prior to the initiation of tofacitinib will be used, as long as the prior visit occurred within four months of the tofacitinib start date. Initiations that occur between visits and where the prior visit is greater than 4 months from the initiation will be excluded.

4.4.3.2. *Multiple visits in the same time window*

Given the observational nature of the data, it is possible for patients to have more than one visit that falls within a given follow-up period’s allowed time window. For example, a patient might have a visit with outcomes collected at 5 months and then 9 months, both of which would qualify as a “6-month” visit. In that case, the latest visit will be chosen as the “6-month” follow-up since we would like to consider the longest follow-up possible. The exception to this rule is if values for the primary outcome are unavailable for the latest visit, in which case the first visit will be used instead.

4.4.3.3. *Discontinuations prior to follow-up*

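### The tofacitinib discontinuation percentage is read at a visit anywhere from 3 to 9 months, latest preferred, so it is not a 6-month risk; report a fixed-day estimate from tofacitinib start

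*SAP*

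**What the plan says.** SAP 4.4.5.2 and Protocol 9.4.2 both list the "Number (%) of tofacitinib discontinuations prior to or at 6-month visit" as the last secondary outcome for the 6-month objective.

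SAP 4.4.3 defines the 6-month follow-up as a "clinical visit to the rheumatologist 3 to 9 months from the enrollment visit in accordance with the Registry protocol"; Protocol 9.4 says the same. When several visits qualify, the latest is taken "since we would like to consider the longest follow-up possible". The exception is when "values for the primary outcome are unavailable for the latest visit, in which case the first visit will be used instead".

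SAP 4.4 starts the clock elsewhere: "The index date will be defined as the date of tofacitinib initiation at or after enrollment in the registry".

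SAP 4.4.7.2 describes dichotomous outcomes by frequencies and proportions with 95% confidence intervals, and adds that the number of patients stopping tofacitinib will be summarized. Neither document sets a fixed day for counting stops, uses person-time or a time-to-event method, or asks for the distribution of visit times. The carry-forward rule in SAP 4.4.3.3 deals with clinical and patient-reported values and leaves time at risk as it is. SAP Table 3 has no row for discontinuation.

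**The concern.** A wide visit window is a sensible tolerance for a measurement such as CDAI, which exists only where there is a visit. Discontinuation is different: the proportion who have stopped can only rise with the time observed. A patient read at 3 months has had half the nominal time in which to stop, and one read at 9 months has had one and a half times that. A single percentage pools them as if they shared one horizon.

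Two visit rules add to this. Preferring the latest visit lengthens the horizon for patients who are seen more often. The exception for a missing primary outcome makes the horizon depend on whether CDAI was recorded.

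The figure will naturally be read as the share who stopped by 6 months. In a descriptive study the percentage is itself the result, so a reader needs to know which horizon it refers to.

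**Working it through.** **Inputs from the documents.** The window is 3 to 9 months with the latest visit preferred (SAP 4.4.3). About 107 patients have CDAI at baseline and 6 months (SAP 4.4.9), taken here as an approximate denominator.

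**Assumptions.** The documents give no discontinuation rate and no visit spacing. I assume a true 6-month risk R of 20%, 30% or 40%, a constant hazard, and several visit schedules. The plan states no figure for this outcome, so there is none to reproduce.

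**Step 1: spread of horizons.** Counted from tofacitinib start, 9/3 = 3, so the horizon varies up to threefold. This is the scheduled observation time; a stopper's own time at risk ends at the stop.

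**Step 2: the anchor.** Read literally, the window runs from enrollment while risk starts at initiation. A patient who starts tofacitinib 8 months after enrollment and is seen at month 9 has 9 − 8 = 1 month at risk. A patient who starts more than 9 months after enrollment has no qualifying visit. On that reading the 3-month floor disappears.

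**Step 3: extremes.** With a constant hazard, h = −ln(1 − R)/6 and F(t) = 1 − exp(−h·t) = 1 − (1 − R)^(t/6). For R = 30%:
- t = 3: 1 − 0.7^0.5 = 16.3%
- t = 9: 1 − 0.7^1.5 = 41.4%

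The same formula gives 10.6% and 28.4% for R = 20%, and 22.5% and 53.5% for R = 40%. A front-loaded hazard (Weibull, shape 0.7) narrows the range for R = 30% to 19.7% and 37.7%. These values would need every patient to be read at the same window limit.

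**Step 4: averages under plausible timing.** If one visit per patient falls uniformly over 3 to 9 months, F averages 29.6% for R = 30%, so there is almost no bias. The later of two uniform visits averages 33.8%, about 4 points too high.

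The next table comes from a simulation of 200,000 patients. Visit intervals are uniform, counted from tofacitinib start, and the latest in-window visit is used. Repeat runs agree within about 0.2 points. The excess over R is in brackets.

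| Visit interval | R = 20% | R = 30% | R = 40% |
|---|---|---|---|
| 2–4 months | 23.9% (+3.9) | 35.3% (+5.3) | 46.4% (+6.4) |
| 3–6 months | 21.3% (+1.3) | 31.7% (+1.7) | 41.9% (+1.9) |
| 4–8 months | 20.3% (+0.3) | 30.4% (+0.4) | 40.4% (+0.4) |

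With the 2–4 month interval, the visit used falls at a mean of 7.4 months.

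**Step 5: sampling error.** The 95% half-width is 1.96·√(R(1 − R)/107), which gives 7.6, 8.7 and 9.3 points for R = 20%, 30% and 40%. Each simulated excess is smaller than the matching half-width.

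**The case against.** The strongest reply is that the plan is open about its window and gives the reason: registry visits are not evenly timed. It counts stops up to the visit and never calls the result a 6-month risk. The outcome is the last of the secondary outcomes in a single-cohort descriptive study with no hypothesis. Two of the three simulated schedules give a bias of 2 points or less, and even the densest stays inside the sampling error. That schedule has no support in the text. All three schedules also give every patient an in-window visit, whereas only about 107 of about 376 patients with baseline CDAI (28%) also have it at 6 months. Table 1 already lists duration of tofacitinib use, which tells the reader something about time on drug.

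Most of this stands, and it limits the size of the point. A reader might infer from the 3- and 9-month values that the reported figure could plausibly be anywhere from 16% to 41% when the truth is 30%. The documents do not support that, because it needs all visits at one limit. A reader might also infer that the figure must be too high. That does not follow either: the latest-visit rule acts only on patients with more than one visit in the window, and the enrollment anchor can shorten the time at risk. Nor is threefold a firm upper bound, since it assumes a clock from tofacitinib start.

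Two things are not answered. A shift due to visit timing is systematic, and the confidence interval does not show it. And without the distribution of visit times, no reader can judge how large it is. Mean duration of use does not supply the horizon at which stops were counted.

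**Conclusion.** The point holds as a matter of definition and reporting. The crude percentage is cumulative to a visit whose timing differs between patients, so it does not estimate a 6-month risk, and nothing in the plan corrects for this or lets a reader see it.

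Its likely size is modest: from under 1 point to about 4 to 6 points too high, against a half-width of about 8 to 9 points. That rests on a constant hazard, assumed 6-month risks of 20% to 40%, assumed visit intervals, a clock from tofacitinib start and about 107 patients. If the enrollment anchor is applied literally, horizons are less uniform still, and neither the size nor the direction of the bias can be stated from the documents. No hypothesis test is affected. A fixed-time estimate is a cheap improvement worth making.

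**What to change.** 1. Reconcile the anchor in SAP 4.4.3 and Protocol 9.4, so that the follow-up window and the index date use the same starting point.
2. Report the Kaplan-Meier probability of having discontinued tofacitinib by a fixed day from tofacitinib start, for example day 183, with a 95% confidence interval, censoring at the last Registry visit.
3. Do this in all eligible initiators with any post-index follow-up. The Aim 2 subset is selected on having a 6-month visit (SAP 4.4.2), while Protocol 9.2.1 also admits patients who stop at a visit before the window. In that subset, a Kaplan-Meier estimate would still not be 6-month persistence.
4. Keep the raw count, label it *by the 3–9 month visit*, and add the missing discontinuation row to Table 3.
5. Report the median (IQR) time from tofacitinib start to the visit used.

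The cost is one extra estimate, one table row and one summary line. The SAP already uses a tofacitinib start date, separates stops at visits from stops between visits, and tabulates duration of use, so the timing data appear to be available. The downside is that stop dates between visits may be approximate. The estimate also assumes that patients whose Registry visits end early are no more or less likely to stop than those still followed.
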